E. Prospective Study: All sites will begin recruiting patients by the beginning of study Month 13. As most cancer programs have at least rudimentary patient tracking and navigation, this degree of usual care will serve as the control. All providers will receive the co-morbid illness educational checklist at all sites and will receive monthly data concerning surgical rates by comorbid condition and race. Patients will be randomized to either usual care or a more intense communication intervention delivered by a trained cancer communication educator as described below. Since we are building on the methods of our prior cohort study, pretesting of recruitment methods and study instruments can proceed quickly before randomization. Lung cancer surgery rates in the control groups will be compared to historical controls at the individual sites to account for a passive effect of the registry and educational checklist. As care registries and data compilation by race is a mandate of the HITECH portion of the American Recovery and Reinvestment Act, we don't believe that it's ethical to deny any group access to the registry. Given the flat rate of lung cancer surgery and persisting racial gap documented for over a decade in datasets of national scope [7, 36, 38], historical controls for this portion of the study are justified.

1. Inclusion and Exclusion Criteria for Patients

We will enroll patients who meet these criteria: (1) age 21 years or greater; (2) a probability of 60% or higher of a lung lesion being malignant as calculated by Bayesian analysis derived from clinical and radiographic criteria or, alternatively, biopsy proven disease; and (3) the patient has received a clinical classification of stage I or II disease. By "clinically classified", we mean using all studies including CT scans, PET scans, bone scans, mediastinoscopy, and / or any study or procedure performed short of thoracotomy.

We will exclude patients from this study for 3 reasons: (1) incarceration / ward of the state status, (2) severe cognitive impairment, (3) absolute contraindications by pulmonary function testing, or (4) Non-English speaking. Hispanic patients represent less than 4 percent of lung cancer patients in North Carolina restricting our ability to document an intervention effect.

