
B. Data Feedback – Results of the retrospective chart review will be distributed to and reviewed with all lung cancer care providers at their participating institutions. Particular emphasis will be placed on the role of co-morbid conditions and outcomes according to race (VII). Since small clusters of physicians perform nearly all lung cancer care in each health system, cross-contamination for any physician-specific intervention is very likely. Therefore, prospective physician feedback will be delivered at all institutional sites. Cumulative data feedback that includes race, co-morbidity variables and surgical rates will be presented to lung cancer providers *by an identified physician champion at each clinical site* quarterly. “Drop outs” and negative provider recommendations will be flagged in real time. The clinic champion will arrange intensive clinical review if the barrier stems from clinical recommendations while the CCE will re-examine patient related barriers. Current IT systems at cancer care organizations do not often factor in patient race, track “real time” clinical performance, generate regular provider reports or suggest options for improvement (V). Although routine quality improvement has not always been effective in addressing disparities [28], we will create a race-specific registry for our study patients similar to the effective registry that Bickell et al. [16] employed for adjuvant breast cancer therapies. We will follow the effect of the registry function via historical controls.

- C. Registry development – note that [name] and [name] have past experience designing a diabetes registry with care flags and point of care reminders that is utilized for paper-based practices in a statewide quality improvement project (formally IPIP, now the North Carolina Healthcare Quality Alliance). The same electronic backbone will be used to track appointments, procedures, adherence and recommendations related to care for early stage, non-small cell, lung cancer.

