
hypothesis 1b. the communication intervention will be more effective in patients who score lower in measures of health literacy

Using the logistic regression analyses for clustered data as noted above, the interaction effects of health literacy, S-TOFHLA scores, and intervention group will be tested in all models. . S-TOFHLA scores will be tested as a continuous variable and also, separately, as a dichotomous variable comparing those categorized as inadequate or marginal literacy with those categorized as adequate literacy [103]. Cumulative pre-intervention surgical rates will be compared at all sites with post-intervention rates using Pearson's chi-square test. Post-intervention rates will be compared using test of proportions and changes in proportions from baseline will be compared between surgical and nonsurgical groups using appropriate methods. To determine if the post-intervention rate approaches maximal surgical rates, we will identify patients with high risk co-morbidities, above the age of 80, and need for pneumonectomy or multiple lobectomy in the "no surgery group", subtract this sum from the denominator then re-calculate the surgical rate. We will analyze the secondary specific aim, To measure the effect of the intervention on patients' perceptions of communication and satisfaction with care, by dichotomizing these variables and replacing surgery as the dependent variable in chi-square and logistic regression models as described under the specific aim above.

Specific Aim 2. To reduce the documented difference in lung resection surgery and mortality between African-American and White patients with early stage, non-small cell

lung cancer.

hypothesis 2a. giving physicians who make lung cancer surgery decisions data relating co-morbidity to surgical outcomes will reduce racial differences in surgery

hypothesis 2b. using a real time lung cancer registry to provide physicians race-specific feedback about their surgical treatment of early stage lung cancer patients will reduce racial differences in surgery

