We will analyze patient level cross-sectional dichotomous outcome data using logistic regression growth models. We will both limit analyses to the cancer communicator control group and do an all enrollee analysis by adding a communicator intervention / no communicator intervention predictor variable to the models. First, we will fit a saturated growth model to estimate annual proportions of these outcomes, before and after the registry/feedback intervention, to assess the effects of the intervention on these outcomes by contrasting the proportions before and after the interventions. We will test the null hypothesis that the proportions before and after the intervention are the same. We will repeat this analysis by including "race" and "race x time" interaction in this model to examine changes in these outcomes between the two races and also if there are any differential changes over time. We will test the null hypothesis that the proportions before and after the intervention are the same for each race

Data interpretation: If our data feedback / registry intervention is found to produce an effect in less than the 4 Cancer Centers, it will prompt further examination of the factors that moderate or mediate the relationship between the intervention and completion of cancer treatment. Thus, by conducting an embedded randomized cohort-control study of the Cancer Communicator intervention component, we may be better able to provide more information about the dimensions along which these interventions can or cannot be generalized.

hypothesis 2c. a cancer communicator who utilizes active listening and teach-back methods during discussions about lung cancer surgery with newly diagnosed, early stage patients will increase the rate of surgery in African-American patients more than Caucasian patients compared to usual care.

We will compare post intervention, unadjusted, surgical rates between African-American and White lung cancer patients using chi-square analysis as discussed under Aim 1. We will also perform the maximum rate analysis stratified by race. The regression models described above under Aim 1. We will also apply these analyses to patients in the communicator group alone selecting patients on an intention to treat basis.

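### Hypotheses 2a (co-morbidity data) and 2b (registry feedback) share one before/after contrast and reach every provider, so the stated analysis cannot credibly separate them

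*SAP*

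**What the plan says.** SAP section 6, Specific Aim 2, lists the two provider-level hypotheses separately. Hypothesis 2a is that "giving physicians who make lung cancer surgery decisions data relating co-morbidity to surgical outcomes will reduce racial differences in surgery". Hypothesis 2b predicts the same result from "using a real time lung cancer registry to provide physicians race-specific feedback about their surgical treatment of early stage lung cancer patients".

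One analysis paragraph follows both. It fits logistic growth models to annual proportions "before and after the registry/feedback intervention, to assess the effects of the intervention on these outcomes", then repeats the fit with race and race x time. It is to be run in the communicator control group alone and in all enrollees with a communicator term.

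The protocol describes delivery:

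- Section E: "All providers will receive the co-morbid illness educational checklist at all sites and will receive monthly data concerning surgical rates by comorbid condition and race".
- Interventions, item B, on the chart review: "Results of the retrospective chart review will be distributed to and reviewed with all lung cancer care providers at their participating institutions".
- Interventions, item B, on feedback, after noting that cross-contamination between physicians is very likely: "Therefore, prospective physician feedback will be delivered at all institutional sites".
- Section E, on withholding: "we don't believe that it's ethical to deny any group access to the registry".

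Only the communicator is randomized. Section E compares the control group with site-level historical controls, to account for the registry and the checklist jointly.

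**The concern.** Two hypotheses that name different components need two contrasts, or at least some patients exposed to one component without the other. The documents plan neither. No site, arm or analysed period has co-morbidity data without registry feedback, or the reverse. The components also overlap in content, because the prospective feedback itself reports co-morbidity along with race and surgical rates.

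If the Black/White gap narrows, the plan as written allows that one result to be reported under both 2a and 2b. A health system choosing between a checklist and a registry would then be told that each works, on evidence that cannot tell them apart. Aim 2 also feeds the interim rule at the end of SAP section 6, under which documented benefit on surgical rates and disparities ends the study. What an Aim 2 result can support should be settled beforehand.

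**Working it through.** **The plan's own figures.** SAP section 7 gives no power for 2a, 2b or any race x period term. Its headline figure is 80% power for 0.63 to 0.69 with n = 496. This reproduces with power = Φ{[(p1 − p0) − 1.96·√(p0(1−p0)/n)] / √(p1(1−p1)/n)}:

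- √(0.63·0.37/496) = 0.02168, and 1.96 times this is 0.0425.
- √(0.69·0.31/496) = 0.02077.
- (0.06 − 0.0425)/0.02077 = 0.843, so power is 80.0%.

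The same formula gives 80.8% for 159 Black patients (0.55 to 0.66) and 78.9% for 337 White patients (0.66 to 0.73). The figures are sound, but they concern overall rates against the previous study and do not bear on separating 2a from 2b.

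**Exposure, side by side.**

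| Group with outcome data | Co-morbidity data/checklist | Registry feedback | Communicator |
|---|---|---|---|
| 2008-2009 charts (protocol section D) | no | no | no |
| Enrolled, usual care | yes | yes | no |
| Enrolled, intervention | yes | yes | yes |

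The two component columns are identical. Chart-review results may reach providers before recruitment starts (by Month 13), but the planned outcome data are the charts and the enrolled patients, so no period with co-morbidity data alone is observed.

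**Rank check.** Cells are 4 sites x 2 races x the 3 groups above, or 24 rows. Base columns are the intercept, 3 site terms, race, communicator and race x communicator: 7. Let A be the co-morbidity data and B the registry feedback.

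| Model | Columns | Rank |
|---|---|---|
| Base + one package term + its race interaction | 7 + 2 = 9 | 9 |
| Base + A, A x race, B, B x race | 7 + 4 = 11 | 9 |
| The same + the patient-level co-morbidity list | 12 | 9 |

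The package change and its difference by race can be estimated; the split between A and B cannot. The patient-level list in Interventions, item D, does not help. It concerns African-American intervention-arm patients who have dropped out of care, and it goes through the communicator. Coded at arm level it equals race x communicator, and at patient level it follows a post-randomization event.

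**Allowing for timing.** Suppose A starts as a step and B accumulates as 0, 0, 1, 2, 3 over two chart years and three recruitment years. This coding is an assumption; the plan gives none.

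- Without year terms, the 11 columns have rank 11. B is then simply a linear trend after the step, so any drift during recruitment would be credited to feedback.
- The SAP calls for a saturated model of annual proportions. That adds 4 year terms and 4 race x year terms: 7 + 8 + 4 = 19 columns, rank 15. Base and year terms alone already give 15, so A and B add nothing once years are free.

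**Usual-care group alone.** Without communicator columns, separate A and B terms give 9 columns and rank 7. Restricting the group removes the communicator effect and leaves A and B tied.

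**The case against.** The strongest reply is that the documents already treat the provider components as a bundle. Section E pairs the registry and checklist, the Aim 2 analysis speaks of one registry/feedback intervention, and Aim 3 addresses all elements together. Bundling is also justified, by cross-contamination and by the ethics of withholding the registry. The race x time model in the control group is already planned, and no passage promises separate estimates. This stands as far as it goes: the model needs little change, and a double claim is a risk of the wording rather than something the sponsor has announced. But package language elsewhere does not withdraw 2a and 2b, and Aim 3 adds the communicator to the bundle.

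The second reply concerns timing. The chart review is done in the first six months, whereas feedback is cumulative (monthly in section E, quarterly in Interventions, item B) and builds only as patients enrol. A reader might infer from the shared contrast that the separate effects have no estimate at any sample size. The documents do not support that, since it assumes both components start as one identical step, and coding the accumulation can make the columns differ. What survives is narrower: any such separation would be non-randomized, is not pre-specified, and depends on assuming no calendar trend or a fixed shape for one.

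**Conclusion.** Under the stated analysis, the effects in 2a and 2b cannot be credibly separated. There is one contrast for two hypotheses, a rank deficit of two when both components are coded as the plan's single before/after step, and no added information from timing once years are free. This rests on delivery to all sites as described, with no planned stagger, and on the 2008-2009 charts serving as the before period.

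A reader might also infer that the package effect is cleanly identified once the hypotheses are merged. It is not. The baseline is charts selected by billing codes. Enrollees have consented, may lack a tissue diagnosis and may have been found by CT search. Secular change and these population differences remain in the estimate.

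The primary comparison under 1a rests on the randomized communicator and is untouched. The point is worth correcting because it changes what Aim 2 may conclude, at almost no cost.

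**What to change.** In SAP section 6, Specific Aim 2:

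1. Replace 2a and 2b with one hypothesis: the combined provider-level package (chart-review data, checklist and registry feedback) reduces the Black/White difference in surgery.
2. Name the race x period interaction as its test, in the usual-care group against the 2008-2009 chart baseline.
3. Keep the planned all-enrollee model with a communicator term as the supporting analysis. Dropping it would discard the intervention-arm patients for no gain in separating components.
4. State that component effects cannot be separated, and that the package effect is a historical comparison open to secular change and to differences between charted and enrolled patients.

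The cost is one fewer claim. The models are already in the SAP, and no new data or change of design is needed. Keeping two hypotheses would require staggered or factorial delivery. With the components varied over the 4 sites (both, first only, second only, neither), the model reaches rank 13 of 13. That leaves one site per cell and little precision, and it conflicts with the protocol's reasons for giving the registry and feedback to everyone.

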Lung Cancer Surgery: Decisions Against Life Saving Care - The Intervention

NCT01687738

Protocol Date: May 13, 2011

Most Recent IRB Approval Date: March 29, 2016

Lung Cancer Surgery: Decisions Against Life Saving Care - The Intervention

STUDY PROTOCOL

A. Overview: We propose a multiple site, imbedded randomized clinical trial. Overall lung surgery rates and black / white disparities have not improved during a decade of documentation [38]. We will establish baseline rates of surgery at each site accounting for race and co-morbid illness using a 2-year retrospective chart review. All patients with Stage I or II non-small cell lung cancer who enroll in the study will be entered into real time registries at every site and patients' progress through the registries including follow-up provider visits, diagnostic tests, and procedures will be transparent to lung cancer providers. The randomized trial will compare patients who receive usual care to those who receive visits and calls from a trained cancer communicator who is well versed in issues specific to lung cancer and trained in active listening and communication that accounts for patients' limitations in health literacy.

B. Description of the Study Areas: The proposed study area is comprised of 3 North Carolina sites (Chapel Hill, Greensboro, and Greenville), in addition to Columbia, South Carolina (Appendix G). One is purely staffed as an academic medical center (AMC) for which the hospital has no community staff members, two have a mix of academic-based and community practices, and one consists entirely of community practices. In addition to the mix of practice settings, both urban and rural geographic settings with large African-American populations will be included. We have successfully recruited at all 4 sites in our recent prospective study. The selection of these sites was motivated by 4 considerations: (i) the university hospitals have large referral bases that concentrate many lung cancer patients in a few focused areas. ECU and the MCHS are partners in the community engagement core of the UNC CTSA. We will take advantage of CTSA infra-structure to execute a multi-modal intervention that will translate into improved lung cancer care. We will also involve the education core of the CTSA to help train students and fellows interested in cancer-related translational research.

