C. Early Stage, Non-Small Cell, Lung Cancer Cases: The table below includes number of patients from 2007 with stage I and II, non-small cell lung cancer entered in each local cancer registry. These data only include patients with tissue proven diagnoses and not those who had CT lesions with extremely high cancer probability and refused surgery or dropped out of follow-up (we did include these patients in our prospective study). Therefore, eligible patients are underestimated while "percent surgery" rates are overestimated when factoring in all patients with early stage, non-small cell disease.

Site	Number of Cases	African-Americans	Percent Surgery
ECU	63	11	70
MCHS	141	24	69
UNC	57	14	74
USC	66	17	75

From our prospective study, we anticipate an average recruitment rate of 70% across sites. Only 11% of all patients approached during the post-diagnosis – pre-treatment recruiting interval refused participation and there was no difference by race.

D. Retrospective Chart Review: Our recently completed study demonstrated that co-morbid

conditions differentially affected black patients' care. Given these data, during the first six months of the intervention trial we will perform a retrospective chart review for the 2008 and 2009 calendar years. We will review all patients diagnosed with stage I or II, non-small cell cancer to serve as a baseline for surgical rates and to examine outcomes of patients treated with and without surgery using a very specific analysis of co-morbid conditions and severity. These data will be checked against Strand's report [45] to assess compatibility and level of detail. The results will be used by our expert panel of co-investigators and site investigators to create an educational checklist to remind lung cancer providers that surgical contra-indications are often relative and subjective. We anticipate the availability of approximately 100-150 charts per site in the 2-year pre-study window. Charts will be selected using appropriate ICD-9 billing codes. Data will be collected in an aggregate manner and no linkage files or specific patient identifiers will be maintained.

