Lung Cancer Surgery: Decisions Against Life Saving Care - The Intervention

NCT01687738

Protocol Date: May 13, 2011

Most Recent IRB Approval Date: March 29, 2016

Lung Cancer Surgery: Decisions Against Life Saving Care - The Intervention

STATISTICAL ANALYSES

Outcome Measures

Primary Outcome. Whether or not patients undergo lung resection surgery represents the main study outcome. We will conform to the 4 month standard used in the SEER database. To ascertain the result, we will first call patients' physicians to determine whether surgery occurred within the designated time frame. Given the possibility that individual patients could seek other opinions and receive surgical care elsewhere, when appropriate, we will ask the patient, or a family member (if the patient is dead or unavailable), whether surgery was performed by someone other than the index physician. If surgery has not occurred, we will ask for reasons. Through appropriate consent, we will retain the option of confirmatory medical records review. For secondary analyses, we will record surgeries that occur beyond the 4 month threshold.

Secondary Outcomes.

1. One year, post-enrollment survival in surgical and non-surgical groups
2. Satisfaction of patients that received interventions compared to those who did not
3. Patients' perceptions of communication for those patients that received intervention compared to those who did not
4. SF-12 scores at baseline, 6 months post-enrollment and 12 months post enrollment

6. Data Analysis:

Our current plan includes:

Descriptive statistics (means, standard deviations, frequencies, proportions, correlations, and graphical displays) will be computed for all study variables at baseline and post-baseline. The distribution of all outcome variables will be assessed to determine if distributional assumptions are valid. Descriptive statistics will be obtained for all the variables overall and by race and site. Statistical methods for addressing each of the specific aims of the study are detailed in this section. Since several statistical tests are planned, there is the possibility of incurring spurious results if we do not correct for multiple comparisons. All tests are based on a 2-sided alpha of 0.05.

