The SF-12 physical and mental component scores will be converted to 0 – 100 scales and utilized as the dependent variable. Baseline scores will be compared first to 6 month scores then 12 month scores using paired t-tests. Generalized linear mixed models for repeated measures data will be constructed in a similar manner as the logistic regression models described above; however, surgical status, race, and comorbid conditions will be forced predictors in these model.

Note that interim analyses regarding specific aims 1 and 2 will be performed at the end of study year 2 then annually. If statistically significant benefits in care are documented on surgical rates and reduction in disparities, the study will be terminated and workshops and individual training sessions of the communication methodologies will be initiated for the care teams at all the study sites.

7. Sample Size

Power computations are computed for post-intervention comparison of proportions. The project anticipates enrolling 496 patients into the study due to constraints on budget, patient availability, and study duration. Thus, we compute the minimal effect size we can detect with statistical power of 80% for our primary aim, AIM 1, using the specified sample size. In computing the effect size, we specify our main outcome as the probability of undergoing surgery for all patients post-baseline as compared to the probability for all patients in the previous study because all groups will receive the data registry and feedback interventions.

Let p_1 be the proportion all patients who undergo surgery in the present study and $p_0 = 0.63$ be the proportion of patients who underwent surgery in the previous study. Using a one-sample test of proportion with 496 subjects overall and significance level of 0.05, we have 80% power to detect a minimally important difference (increase) in surgical rate of $p_0 = 0.63$ to $p_1 = 0.69$. With a sample size of 159 for blacks, we have 80% power to detect an overall increase from $p_0 = 0.55$ (as measured in the previous study) to $p_1 = 0.66$ with significance level of 0.05. With a sample size of 337 for whites, we have 80% power to detect an overall increase from $p_0 = 0.66$ (as measured in the previous study) to $p_1 = 0.73$ with significance level of 0.05.

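### The before/after growth model for hypotheses 2a and 2b omits co-morbid illness, so a change in case mix between the historical charts and the enrolled patients is read as an effect, or as no effect, of registry and feedback

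*SAP*

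**What the plan says.** **The model.** For hypotheses 2a and 2b the SAP (6. Data Analysis, Specific Aim 2) states: "First, we will fit a saturated growth model to estimate annual proportions of these outcomes, before and after the registry/feedback intervention". It is run once in the communicator control group alone and once in all enrollees with a communicator indicator. Race and race-by-time are then added. No other covariate is named, and nothing refers back to the Aim 1 covariate list.

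**What other sections say about co-morbidity.**
- Protocol A (Overview): "We will establish baseline rates of surgery at each site accounting for race and co-morbid illness using a 2-year retrospective chart review".
- Protocol D (Retrospective Chart Review): charts are examined "using a very specific analysis of co-morbid conditions and severity".
- Protocol E.4.B (Data Feedback), for the prospective period: "Cumulative data feedback that includes race, co-morbidity variables and surgical rates" are reported to providers.
- SAP Aim 1 forces co-morbid illness into its model, Aim 3 controls its before/after comparison for the Aim 1 variables, and Aim 4 forces in co-morbid conditions.

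**The two populations.** The chart review (Protocol D) takes every stage I or II diagnosis in 2008 and 2009. The prospective cohort (Protocol E.1 and E.2) consists of consenting patients. It excludes those whose lung-function tests absolutely rule out surgery, admits lesions with a malignancy probability of at least 60%, and adds patients found by the CT search.

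**The concern.** Randomisation protects the comparison of communicator with usual care. It does not protect the comparison of historical charts with enrolled patients, which is how hypotheses 2a and 2b are tested. If the enrolled patients carry more or less co-morbidity than the chart patients, the surgery rate moves for that reason alone, and the model attributes the movement to registry and feedback.

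The direction cannot be predicted. The lung-function exclusion removes patients unlikely to have surgery and raises the enrolled rate. The CT search may bring in patients who resist surgery and lower it. A false gain and a hidden gain are both possible.

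The consequence goes beyond one secondary result. The SAP (end of the Specific Aim 4 text) plans interim analyses of Aims 1 and 2, and stops the study if benefits on surgical rates and disparities are statistically significant.

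**Working it through.** **1. The plan's own figure.** The SAP (7. Sample Size) writes "Using a one-sample test of proportion with 496 subjects overall and significance level of 0.05" and "we have 80% power to detect a minimally important difference (increase) in surgical rate of" 0.63 to 0.69. The one-sample formula is n = [1.96·√(p0(1−p0)) + 0.84·√(p1(1−p1))]² / (p1−p0)². With 0.63 and 0.69 it gives n = 496 and power 80.0%, so the figure reproduces two-sided, in line with "All tests are based on a 2-sided alpha of 0.05". It treats 0.63 as known without error. The SAP gives no power for the growth model.

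**2. Sample sizes for the growth model.**
- Before: 100 to 150 charts per site at 4 sites, so 400 to 600. I use 500.
- After: "The project anticipates enrolling 496 patients into the study due to constraints on budget, patient availability, and study duration". Every historical chart has communicator = 0. In the all-enrollee version the indicator absorbs the difference between arms, so the before/after contrast rests on the controls in both versions.
- The allocation ratio is not stated. Assuming 1:1, there are 496/2 = 248 controls.

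**3. Assumed case-mix shift.** The documents give no surgery rate by co-morbidity. Suppose 75% of patients without and 45% of patients with major co-morbidity have surgery, and prevalence goes from 30% to 40%.
- Before: 0.30×0.45 + 0.70×0.75 = 0.66
- After: 0.40×0.45 + 0.60×0.75 = 0.63
- The rate falls 3 points with no true change.

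**4. Rejection with no true effect.** SE = √(q0(1−q0)/500 + q1(1−q1)/248), and the rejection probability is P(|Z + shift/SE| > 1.96).

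| Rates | Shift | SE | Shift/SE | Rejection |
|---|---|---|---|---|
| 0.64 to 0.63 | 1 point | 0.0374 | 0.27 | about 6% |
| 0.66 to 0.63 | 3 points | 0.0373 | 0.80 | about 13% |
| 0.63 to 0.57 | 6 points | 0.0381 | 1.57 | about 35% |

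The 1-point row assumes a 20-point co-morbidity gap (70% v 50%) and prevalence 30% to 35%. The 6-point row assumes a 40-point gap (75% v 35%) and 30% to 45%.

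**5. Masking.** For a true rise from 0.63 to 0.69, SE = √(0.63×0.37/500 + 0.69×0.31/248) = 0.0365. Then 0.06/0.0365 = 1.65 and power is about 38% (36% with a pooled variance). If a 3-point shift leaves 0.63 to 0.66, SE = 0.0370, the ratio is 0.81 and power is about 13%.

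**6. Effect of adjustment.** I simulated 500 charts against 248 controls with surgery rates of 75% and 45%, 2,000 runs per setting.
- Prevalence falling from 40% to 30%, no true effect: the unadjusted model rejects in 12% of runs, the co-morbidity-adjusted model in about 5%.
- True log-odds effect 0.30, prevalence rising from 40% to 50%: the unadjusted model estimates 0.15 with 15% power, the adjusted model 0.30 with 40% power.

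**7. The eligibility difference.** Suppose chart patients with absolute lung-function contraindications never have surgery. Removing a share x turns 0.63 into 0.63/(1−x). A share of 1 − 0.63/0.69 = 8.7% produces the whole 63% to 69% change.

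**8. Race-by-time.**
- The same 30% to 40% prevalence shift in both races, with 101 Black patients among 500 charts (66/327 = 20.2% in the Protocol C table), 159 Black and 337 White enrollees, and Black v White co-morbidity gaps of 30 v 30, 40 v 30 or 30 v 20 points: rejection stays at 5.0% to 5.1%.
- If contraindicated charts are 10% of Black and 5% of White charts, the SAP's rates of 0.55 and 0.66 become 0.55/0.90 = 0.611 and 0.66/0.95 = 0.695. The gap falls from 11.0 to 8.4 points with no intervention effect.

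**9. Site mix.** Weighted by cases in the Protocol C table: (63×70 + 141×69 + 57×74 + 66×75)/327 = 71.3%. With equal site weights: 72.0%. The difference is 0.7 points.

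**The case against.** **The SAP already plans an adjusted before/after analysis.** This is partly right. Aim 3 controls for the Aim 1 variables, and the text under hypothesis 1b has a further pre/post chi-square test. A reader might infer that the growth model is the only test of registry and feedback, and the documents do not support that. But the chi-square test is unadjusted, and Aim 3 addresses the whole multi-modal package. The growth model is the only analysis specified for 2a and 2b.

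**Hypotheses 2a and 2b concern racial differences, so race-by-time is the term that counts.** This stands as a limit. A reader might infer that any co-morbidity shift inflates the interaction's false-positive rate. Step 8 shows that a shift common to both races leaves it at about 5%.

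**The all-enrollee analysis has 496 patients.** A reader might work from 496, which would raise both the false rejection rate and the power. It would be wrong, because the communicator indicator leaves the time contrast to the controls.

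**Site is handled by GEE.** Allowing for correlation within site does not control confounding by site mix. On the 2007 figures, though, that confounding is worth only 0.7 points.

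**The baseline commitment does not name this model, and the CT-search text speaks of perceived co-morbidity.** Both are true. The Overview sentence concerns baseline rates, and nothing in the documents shows that the enrolled cohort will be sicker. The concern needs only that the populations differ by design, which they do.

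**The intervention aims to change how co-morbidity is interpreted.** The relation between co-morbidity and surgery may therefore change between periods. That is no reason to omit a baseline confounder.

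**Conclusion.** The concern holds. Followed as written, the Aim 2 growth model makes a non-randomised comparison of two differently selected populations without a confounder that is collected in both and included in the models for the other aims.

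The consequence for the before/after contrast is about 13% false rejection for a 3-point shift, with a range of about 6% to 35%. A shift that masks half of a 6-point rise cuts power from about 38% to about 13%. These figures assume 500 charts, 1:1 allocation and the co-morbidity rates shown. The documents give neither the direction nor the size of any real shift.

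No distortion of race-by-time has been demonstrated. It requires a shift, or a share of contraindicated charts, that differs by race. That is possible, since Protocol D reports that co-morbidity affected Black patients' care differently, but it is not quantified anywhere. Site is a minor matter.

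**What to change.** 1. In SAP Specific Aim 2, add to every growth model (control-group-only and all-enrollee, with and without race-by-time) the co-morbidity/severity measure abstracted in the chart review, coded the same way from the prospective records.
2. Base the before/after and race-by-time conclusions on the adjusted contrasts, and report the unadjusted proportions as description.
3. Apply the prospective lung-function exclusion to the charts wherever it is recorded. A covariate cannot remove an eligibility difference.
4. Reconcile Protocol D, which has chart data gathered in aggregate, with the Aim 2 text, which analyses individual patients. De-identified rows, or counts cross-classified by site, year, race, co-morbidity level and surgery, would serve both.
5. A site term is optional.

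The cost is SAP wording, one shared coding form and a few extra parameters. Some bias will remain if co-morbidity is documented more fully in the prospective period, and from eligibility differences that the charts do not record.
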